8.10. Quality Control

Investigators will be trained with an initial on-site visit to the clinic on the protocol, EDC system, site master file, documentation, and any applicable study processes. Any new information relevant to the performance of this NIS will be forwarded to the staff during the study. Remote data monitoring will be conducted during the life of the study to ensure timely reporting of safety data, data integrity, and consistency. eCRFs for all included patients will be made available to the remote data monitor for review. A list of critical variables will be created as required elements for review during the remote data monitoring process. The study sites will be contacted to request resolution to any issues that may arise during the course of the study.

Monitoring visits may be made, if necessary, to monitor study process by Pfizer, Inc. or its delegate. In the event of a visit, direct access to original source data will be required for monitoring visits and/or inspections/audits, which will be carried out with due consideration for data protection and patient confidentiality.

Items routinely checked during on-site visits include:

- Documentation of the informed consent process.
- Compliance with patient eligibility criteria.
- Proper maintenance of records, such as study protocol.
- Completed eCRFs.
- Documentation of adverse events, and transmission of serious adverse events.
- Identification of patients lost to follow up.
- Study correspondence.
- Compliance with IRB approval requirements.

8.11. Limitations of the Research Methods

The source data described in this protocol contain the inherent limitation of any current non-interventional, real world study. These studies have the potential for missing, inaccurate, or incomplete data. The limitations of the observational nature can result in methodological challenges in attributing causality to outcomes. The patient selection and the diagnostic or monitoring procedures are those applied per the usual treatment paradigm of the treating physician and not dictated by the protocol. Heterogeneous patient populations could make the interpretation of the outcomes difficult. Hence, this study is intended for hypothesis generation, as opposed to hypothesis confirmation.

8.12. Other Aspects

Not applicable.

9. PROTECTION OF HUMAN SUBJECTS

9.1. Patient Information and Consent

All parties will ensure protection of patient personal data and will not include patient names on any sponsor forms, reports, publications, or in any other disclosures, except where required by laws. In case of data transfer, Pfizer will maintain high standards of confidentiality and protection of patient personal data.

The informed consent form must be in compliance with local regulatory requirements and legal requirements.

The informed consent form used in this study, and any changes made during the course of the study, must be prospectively approved by both the IRB/IEC and Pfizer before use.

The investigator must ensure that each study patient, or his/her legally acceptable representative, is fully informed about the nature and objectives of the study and possible risks associated with participation. The investigator, or a person designated by the investigator, will obtain written informed consent from each patient or the patient's legally acceptable representative before any study-specific activity is performed. The investigator will retain the original of each patient's signed consent form.

9.2. Patient Withdrawal

Patients may withdraw from the study at any time at their own request, or they may be withdrawn at any time at the discretion of the investigator or sponsor for safety, behavioral, or administrative reasons. In any circumstance, every effort should be made to document subject outcome, if possible. The investigator should inquire about the reason for withdrawal and follow-up with the subject regarding any unresolved adverse events.

If the patient withdraws from the study, and also withdraws consent for disclosure of future information, no further evaluations should be performed, and no additional data should be collected. The sponsor may retain and continue to use any data collected before such withdrawal of consent.

9.3. Institutional Review Board (IRB)/Independent Ethics Committee (IEC)

It is the responsibility of the investigator to have prospective approval of the study protocol, protocol amendments, and informed consent forms, and other relevant documents, (eg, recruitment advertisements), if applicable, from the IRB/IEC. All correspondence with the IRB/IEC should be retained in the Investigator File. Copies of IRB/IEC approvals should be forwarded to Pfizer.

9.4. Ethical Conduct of the Study

The study will be conducted in accordance with legal and regulatory requirements, as well as with scientific purpose, value and rigor and follow generally accepted research practices described in Guidelines for Good Pharmacoepidemiology Practices (GPP) issued by the International Society for Pharmacoepidemiology (ISPE), Good Epidemiological Practice (GEP) guidelines issued by the International Epidemiological Association (IEA), Good Practices for Outcomes Research issued by the International Society for Pharmacoeconomics and Outcomes Research (ISPOR), International Ethical Guidelines for Epidemiological Research issued by the Council for International Organizations of Medical Sciences (CIOMS), European Medicines Agency (EMA) European Network of Centres for Pharmacoepidemiology and Pharmacovigilance (ENCePP) Guide on Methodological Standards in Pharmacoepidemiology, and FDA Guidance for Industry:

Good Pharmacovigilance and Pharmacoepidemiologic Assessment, FDA Guidance for Industry and FDA Staff: Best Practices for Conducting and Reporting of Pharmacoepidemiologic Safety Studies Using Electronic Healthcare Data Sets, Guidance for Industry: Patient-Reported Outcome Measures: Use in Medical Product Development to Support Labeling Claims and/or equivalent.

10. MANAGEMENT AND REPORTING OF ADVERSE EVENTS/ADVERSE REACTIONS

10.1. ADVERSE EVENT REPORTING

10.1.1. Requirements

All observed or volunteered adverse events for which the investigator has determined that the adverse event is related to SU will be recorded as described on the adverse event page(s) of the electronic case report form (eCRF).

For all adverse events, sufficient information should be obtained by the investigator is to determine the causality of the adverse event. The investigator is required to assess causality.

For adverse events with a causal relationship to SU, follow-up is required until the event resolve; and Pfizer concurs with that assessment.

If a serious adverse event occurs, expedited reporting will follow local and international regulations, as appropriate.

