8.9. Data Analysis

Detailed methodology for summary and statistical analyses of data collected in this study will be documented in a Statistical Analysis Plan (SAP), which will be dated, filed and maintained by the sponsor. The SAP may modify the plans outlined in the protocol; any major modifications of primary endpoint definitions or their analyses would be reflected in a protocol amendment.

Demographic and other clinical characteristics of the patients will be summarized using the mean, standard deviation, median, minimum, and maximum values, for numeric variables such as age and duration of follow up and frequency distributions for categorical data such as gender. The median and 95% confidence intervals for the main outcomes PFS and TTF will be estimated using the method of Kaplan-Meier. The ORR for adv/mRCC patients receiving SU in the 1st line will be computed along with its 95% confidence interval using the Clopper-Pearson formula. Cox proportional hazard models may be used to explore the potential influences of baseline characteristics on PFS or TTF. A multiple logistic regression model can be used to assess the effect of prognostic variable on ORR.

Change in other variables such as Quality of life and weight at last visit as compared to the baseline will be assessed using the paired t-test at each visit in addition to computing mean differences along with 95% confidence intervals. Moreover, repeated methods can be used to look for trends over time and adjust for possible confounders.

All AEs occurring during the study will be considered as treatment-emergent, and the frequency of AEs will be summarized. Sub-group analyses of association between efficacy outcomes, safety measurements, and baseline factors will be performed for exploratory reasons as needed.

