10.1.2. Reporting Period and Requirements

All adverse drug reactions and other safety information as mentioned below should be documented and reported to Pfizer; for the sake of continuous monitoring of product safety.

Non-AEs and other safety information should be reported to Pfizer, if possible, upon recognition but no later than 10 days.

Patients should be asked to inform the treating physician of any AE or other relevant safety information, immediately. The treating physician has to assess the causal relationship for AEs and report AEs and other relevant drug safety information.

If a SAE occurs that in the opinion of the investigator is related to *Sutent®*, Pfizer is to be notified within 24 hours of awareness of the event and a non-Interventional Study Adverse Event Report Form must be completed and submitted to Pfizer Safety.

In particular, if the serious adverse event is fatal or life-threatening, notification to Pfizer must be made immediately, irrespective of the extent of available adverse event information. This timeframe also applies to additional new information (follow-up) on previously forwarded serious adverse event reports as well as to the initial and follow-up reporting of exposure during pregnancy and exposure during breast feeding and medication error cases.

Suspected adverse reactions that are both serious and unexpected are subject to expedited reporting in accordance with all applicable laws and regulations.

For each patient, the safety event reporting period begins at the time of the patient's informed consent, which is obtained prior to the patient's enrollment in the study, and lasts through the end of the observation period of the study; a report must be submitted to Pfizer Safety (or its designated representative) for any of the types of safety events listed in the table above occurring during this period.

If a patient provides informed consent but is never enrolled in the study (eg, patient changes his/her mind about participation or if patients are screened for eligibility following informed consent, and fail screening criteria), the reporting period ends on the date of the decision to not enroll the patient.

If the investigator becomes aware of a SAE occurring at any time after completion of the study and s/he considers the serious AE to be related to Sutent® (Sunitinib), the SAE also must be reported to Pfizer Safety.

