10.2. DEFINITIONS OF SAFETY EVENTS

10.2.1. Adverse Events

An AE is any untoward medical occurrence in a patient administered a medicinal product. The event need not necessarily have a causal relationship with the product treatment or usage.

Examples of adverse events include but are not limited to:

- Abnormal test findings;
- Clinically significant symptoms and signs;
- Changes in physical examination findings;
- Hypersensitivity;
- Lack of efficacy;
- Drug abuse;
- Drug dependency.

Additionally, for medicinal products, they may include the signs or symptoms resulting from:

- Drug overdose;
- Drug withdrawal;
- Drug misuse;
- Off-label use;

- Drug interactions;
- Extravasation;
- Exposure during pregnancy;
- Exposure during breast feeding;
- Medication error;
- Occupational exposure.

Abnormal test findings

The criteria for determining whether an abnormal objective test finding should be reported as an adverse event are as follows:

- Test result is associated with accompanying symptoms, and/or
- Test result requires additional diagnostic testing or medical/surgical intervention, and/or
- Test result leads to a change in study dosing or discontinuation from the study, significant additional concomitant drug treatment, or other therapy, and/or
- Test result is considered to be an adverse event by the investigator or sponsor.

Merely repeating an abnormal test, in the absence of any of the above conditions, does not constitute an adverse event. Any abnormal test result that is determined to be an error does not require reporting as an adverse event.

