10.2.2. Serious Adverse Events

A serious adverse event is any untoward medical occurrence in a patient administered a medicinal or nutritional product (including pediatric formulas) at any dose that:

- Results in death;
- Is life-threatening;
- Requires inpatient hospitalization or prolongation of hospitalization (see below for circumstances that do not constitute adverse events);
- Results in persistent or significant disability/incapacity (substantial disruption of the ability to conduct normal life functions);
- Results in congenital anomaly/birth defect.

Progression of the malignancy under study (including signs and symptoms of progression) should not be reported as a serious adverse event unless the outcome is fatal within the safety reporting period. Hospitalization due to signs and symptoms of disease progression should not be reported as a serious adverse event. If the malignancy has a fatal outcome during the study or within the safety reporting period, then the event leading to death must be recorded as an adverse event and as a serious adverse event with severity Grade 5.

Medical and scientific judgment is exercised in determining whether an event is an important medical event. An important medical event may not be immediately life-threatening and/or result in death or hospitalization. However, if it is determined that the event may jeopardize the patient or may require intervention to prevent one of the other outcomes listed in the definition above, the important medical event should be reported as serious.

Examples of such events are intensive treatment in an emergency room or at home for allergic bronchospasm; blood dyscrasias or convulsions that do not result in hospitalization; or development of drug dependency or drug abuse. Additionally, any suspected transmission via a Pfizer product of an infectious agent, pathogenic or non-pathogenic, is considered serious. The event may be suspected from clinical symptoms or laboratory findings indicating an infection in a patient exposed to a Pfizer product. The terms “suspected transmission” and “transmission” are considered synonymous. These cases are considered unexpected and handled as serious expedited cases by PV personnel. Such cases are also considered for reporting as product defects, if appropriate.

Hospitalization

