10.3. Causality Assessment

The reviewer of the medical chart will identify all adverse events where an investigator's assessment of causality relative to the use of *Sutent*® (serious and non-serious) is provided in the medical chart. The reviewer of the medical chart must record those adverse events with a causal relationship to *Sutent*® in the eCRF, as appropriate, and report such an assessment in accordance with the serious adverse event reporting requirements if applicable.

An investigator's causality assessment is the determination of whether there exists a reasonable possibility that *Sutent*® caused or contributed to an adverse event. If the investigator's final determination of causality is unknown and the investigator does not know whether *Sutent*® caused the event, then the event will be handled as related to *Sutent*® for reporting purposes. If the investigator's causality assessment is unknown but not related to *Sutent*® this should be clearly documented in the eCRF.

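### The protocol's AE recording rule names SU-related events, but the analyses need all AEs and second-line AEs; a site following the rule alone would undercount both

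*Protocol*

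**What the plan says.** **Recording.** Protocol 10.1.1: "All observed or volunteered adverse events for which the investigator has determined that the adverse event is related to SU will be recorded" on the AE pages of the eCRF. Protocol 10.3: the chart reviewer "must record those adverse events with a causal relationship to" Sutent in the eCRF; this section does not name the AE page.

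**Exceptions in the same chapter.**
- Under 10.2.2, if the malignancy proves fatal during the study or reporting period, "then the event leading to death must be recorded as an adverse event and as a serious adverse event with severity Grade 5".
- Under 10.3, an event whose causality the investigator cannot determine is handled as related "for reporting purposes".
- Also under 10.3, where causality is unknown but judged not related, "this should be clearly documented in the eCRF".

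**Definition and analysis.**
- Protocol 10.2.1 defines an AE broadly: "The event need not necessarily have a causal relationship with the product treatment or usage".
- Protocol 8.9 treats every AE in the study as treatment-emergent and says "the frequency of AEs will be summarized".
- Safety endpoint 7 (Protocol 3.3.3) counts patients on SU with at least one AE, by body system, with no causality limit.
- The SAP's safety endpoints (the list just before SAP 5.4) include incidence by grade for all AEs, then a separate analysis of SU-related AEs.
- The second-line safety objective (Protocol 3.3.2 and 7.1, SAP 2.3) is served by SAP 8.2, which lists AE incidence in the SU–other sequence patients.
- The AE table shell in SAP 9.5 covers the whole study but has one sunitinib column.

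**The concern.** The recording rule describes a subset of what the analyses count. A table of all AEs can be no more complete than what sites enter. If some enter only SU-related events, a reader would take an SU-attributed table as all-cause.

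The second-line objective is the most exposed. An AE attributed only to axitinib or everolimus is not SU-related, and no visible section clearly sends it to the AE page. Discontinuation because of AEs, also an SAP safety endpoint, would be affected for second-line treatment if it is drawn from the same pages.

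The study is descriptive and hypothesis-generating (Protocol 8.11). No test is at risk; what is at stake is what the safety tables can be said to show.

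**Working it through.** **Step 1. Set the texts side by side.**

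| Kind of AE | 10.1.1 and 10.3 taken alone | Needed for the planned output |
|---|---|---|
| Judged related to SU | recorded | yes |
| Causality unknown | handled as related for reporting | yes |
| Fatal malignancy | recorded (10.2.2) | yes |
| Judged unrelated, during SU | no clear instruction to enter it on the AE page | yes (8.9, endpoint 7, SAP all-AE incidence) |
| Attributed only to a second-line drug | no clear instruction to enter it on the AE page | yes (second-line objective, SAP 8.2) |

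The last two rows are the gap. The SAP's separate analysis of SU-related AEs presupposes that other AEs are in the database.

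**Step 2. Direction.** Recording a subset of the events to be counted cannot raise a count. It leaves the count unchanged only if nothing falls in the last two rows.

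**Step 3. Size.** The plan states no AE rate, no share of AEs judged SU-related and no share of patients reaching second line, so there is no AE figure to reproduce. The one design figure, 140 patients (Protocol 8.7), comes from the ORR: 1.96² × 0.37 × 0.63 / 0.08² = 139.9, rounded up to 140. It serves below only as the number enrolled.

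**Step 4. Illustration of counts (all rates assumed).** Let AEs per patient be Poisson with mean m = 2, and let a share r be judged SU-related and recorded. The true share of patients with at least one AE is 1 − exp(−m) = 86.5%. The recorded share is 1 − exp(−m·r), and recorded events are 140·m·r out of 280.

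| r | Recorded events of 280 | Recorded share with any AE |
|---|---|---|
| 0.90 | 252 | 83.5% |
| 0.75 | 210 | 77.7% |
| 0.50 | 140 | 63.2% |
| 0.25 | 70 | 39.3% |

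With m = 1 the true share is 63.2%, and the recorded share runs from 59.3% down to 22.1% over the same r. With m = 4 it is 98.2% against 97.3% down to 63.2%. In second line, with m = 2 and only 5% to 25% of AEs still attributed to SU, the recorded share is 9.5% to 39.3% against 86.5%.

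**Step 5. The denominator matters.** SAP 4.1 defines the safety population as patients with an AE after the first SU dose, so under-recording shrinks it too. Under m = 2 and r = 0.50, its expected size falls from 140 × 0.865 = 121 to 140 × 0.632 = 88.5. Take one AE type that truly affects 56 patients (40% of 140), and let f be the share of those patients whose occurrences are all judged unrelated.

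| f | Recorded patients, 56 × (1 − f) | Over 140 (true 40%) | Over safety population (true 56/121 = 46.3%) |
|---|---|---|---|
| 0.10 | 50.4 | 36% | 56.9% |
| 0.25 | 42 | 30% | 47.5% |
| 0.50 | 28 | 20% | 31.6% |

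Over all enrolled, the percentage falls for every f above zero. Over the safety population it falls only when f exceeds 1 − 0.632/0.865 = 27%; below that it rises.

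**The case against.** The strongest reply is that chapter 10 governs safety reporting while chapter 8 governs data collection, and chapter 8 sets no causality limit. AE assessment appears in the schedule (8.4.1) from baseline to end of study, and among the items to be collected at baseline, in treatment and in follow-up (8.5.1 to 8.5.3). Protocol 8.5 ties collected items to eCRF sections, 8.6 has new and ongoing AEs assessed at each visit, and SAP 2.2 grades the AEs in the eCRF without restriction. Protocol 10.1.2 adds "The treating physician has to assess the causal relationship for AEs and report AEs and other relevant drug safety information". Nor does 10.1.1 forbid entering other events.

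Much of this stands. A reader might infer that the AE page is closed to unrelated events, or that the study will hold no second-line AE data; the documents support neither. But these sections do not displace the explicit rule. Assessing an AE is not the same as entering it, grading applies to whatever was entered, and 10.1.2 concerns reports to the sponsor. A site can read the whole protocol in good faith and settle on either rule.

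Two further inferences should be resisted. Protocol 8.9 does not itself promise second-line AE incidence; that rests on the objective and SAP 8.2. And AE percentages are not bound to be too low, because of how SAP 4.1 defines the safety population.

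**Conclusion.** The instructions conflict, and this is more than missing detail. Where a site follows 10.1.1 and 10.3 alone, AEs judged unrelated to SU are omitted, including those attributed only to a second-line drug, apart from the exceptions in 10.2.2 and 10.3. All-AE and second-line AE counts are then too low.

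That is conditional on how sites read the text. It does not show that undercounting will happen, or that sites will differ. The size cannot be derived; the figures above rest on assumed rates and show only direction and sensitivity. The direction is secure for counts and for percentages over a fixed set of patients, but not for percentages over the SAP safety population.

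Confidence is moderate, because the eCRF, the table of safety events that 10.1.2 refers to, and part of the SAP safety section are not visible and could settle the matter. Even if the eCRF takes all AEs, the protocol text should say so.

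**What to change.** Reconcile 10.1.1 and 10.3 with Protocol 8.9, endpoint 7, the SAP safety endpoints and SAP 8.2.

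**Preferred.** Amend 10.1.1 and 10.3 so that every AE found at the assessments already planned (8.4.1, 8.5.1 to 8.5.3, 8.6) is entered in the eCRF with causality, suspected drug and line of therapy. Tabulate by line in SAP 9.5. Cost: a protocol amendment and some extra data entry, with no new visit. Protocol 10.1.1 already asks investigators to gather enough information to judge causality for all AEs, so the added work is mainly entry.

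**Otherwise.** Keep SU-related capture, title the AE tables as investigator-assessed SU-related AEs, and make no claim on second-line AE incidence. Cost: a narrower safety objective. This also needs an amendment, since Protocol section 4 requires one for any change to the study plan.

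Under either option, state the denominator of each AE percentage.
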